Definition of Pigment qualified for Sklip System	Pigment is defined as any color other than the surrounding skin phototype that delineates a skin lesion from the background that can be visualized with a dermatoscope. This includes: light brown, dark brown, black, white, blue, grey, purple, red, pink, yellow, and orange (including clearly distinguishable vascular patterns within the skin lesion surface area).
Follow-up Duration	After conclusion of the Study intervention, the EMR(s) of all enrolled Participants will be monitored for any relevant data obtained from follow up (as part of standard clinical pathways). An attempt to contact Participants lost to follow-up will be made for up to 30 days.
Duration of Therapy	There is no therapy as part of this Study.
Sponsor Monitoring	The Sponsor will conduct periodic monitoring of the Study Site data handling practices on REDCap Cloud every 45 days on at least one (1) instance to verify the integrity of the source data. This will be done in person or virtually with an approved Study Site representative responsible for REDCap Cloud use and data handling. At the end of the Study, ten percent (10%) of the source data will be re-evaluated by the Sponsor to re-verify the integrity of the source data.
Interim Data Analysis	There will not be any interim data analysis during this Study.
Medical costs during the In-Person Phase	All medical services that fall under the normal clinical care pathway including: scheduling, triage, spot check, FBSE, biopsy, diagnosis and treatment (when applicable), will not be covered by the Study Sponsor and will be billed by Study Sites directly to patient insurance, or required to be paid out pocket.
Final Disposition of the Sklip dermatoscope and Sklip System access	All Participants will be able to keep their Sklip dermatoscope at the end of the Study, at no cost. SMSA access will expire within fourteen (14) days of confirmed delivery of the Sklip dermatoscope at the home address of the Participant.

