Participant Safety	There remains the risk that a Participant may not identify a skin lesion on their body that is malignant (both a PSLC and a non-PSLC). However, all risks are associated with the current at-home standard of care protocol for SSEs and not increased by use of the Sklip System. All Participants are required to come for an in-person FBSE, regardless of if they identify a PSLC during the At-home Phase. The FBSE will ensure that no malignancies are missed.
Synopsis of Statistical Analysis	
An intent-to-treat (ITT) analysis set will include those who are enrolled in the Study regardless of adherence. All primary analyses will be conducted using the intent-to-treat analysis set. Demographic and clinical characteristics will be summarized using descriptive statistics (e.g. proportions, mean/median, and standard deviation/range).
 
The Ground Truth will be the combination of the following:
 
Dataset N) DDI dermoscopic diagnosis ground truth (DDI-GT) for PSLCs that were not biopsied during the In-Person Phase, and

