### 3. STUDY DESIGN

#### 3.1 DESCRIPTION OF THE STUDY DESIGN

*Refer to Section 11, Statistical Analysis for additional information regarding statistical methods used in this Study.*

All Participants of this single-arm prospective trial will be given up to 14 days to **review** the Sklip System instructions, **perform** a self-skin-exam (SSE) at-home, and **identify** PSLCs based on the following:

- (a) General concern (self or partner-identified, or non-dermatology Provider identified requiring a referral to a dermatology Provider)
- (b) Concern because the PSLC is different than the rest (i.e. “ugly duck sign”)

Then, Participants will be instructed to carefully follow provided instructions and **complete** the following for each target PSLC:

- 1) Mark the target PSLC with a green surgical marker (horizontal line) and the number (#) corresponding to the mole log, one (1) inch away from the target lesion
- 2) Record the target PSLC with a number (#) and anatomic location in the PMLS
- 3) Create a new photo album titled: “Moles” in their native smartphone/tablet Photo App
- 4) Take one (1) smartphone clinical image (SCI) of the target PSLC, twelve (12) inches away from the target skin lesion
- 5) Save the SCI in the album titled: “Moles” album
- 6) Review Sklip dermatoscope instructions for proper use
- 7) Take one (1) digital dermatoscopy image (DDI) of the target PSLC using the Sklip dermatoscope.
- 8) Save the DDI of the target PSLC in the “Moles” album
- 9) Upload the DDI to the SMSA (“Scan Moles with Ai”) within the Sklip App once per target PSLC, until either a Suspicious or Unremarkable result is obtained, for a maximum of three attempts. If after three attempts the user still receives an “Error” result, they will be prompted to document this in the participant mole log sheet.
- 10) Take one (1) screenshot of the SMSA output per target PSLC
- 11) Save the SMSA output screenshot in the album titled: “Moles”
- 12) Record each SMSA output (SUSPICIOUS, UNREMARKABLE, ERROR) in the PMLS once per target PSLC
- 13) Contact the Study Site to schedule an in-person FBSE within 28 days, if the Participant does not already have a scheduled visit

In summary, for each target PSLC the Participant will acquire the following:

One (1) smartphone clinical image (SCI)  
One (1) digital dermoscopy image (DDI)  
One (1) Sklip Mole Scanning Algorithm (SMSA) output recorded in the PMLS  
One (1) SMSA output screenshot

---

End of At-home Phase-----

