Study Coordinators at each Study Site will conduct regular EMR chart reviews to track Participant requests to begin their In-person Phase, after the Participant has completed their the At-home Phase. These chart reviews will be conducted systematically every 7 days following Participant enrollment. Participant EMRs will be monitored for up to 28 days following conclusion of both Study Phases to account for any relevant data that may have not been collected during the Study.

---

-----Start of In-person Phase-----

---

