### 5. PARTICIPANT SCREENING, ENROLLMENT, AND WITHDRAWAL

#### 5.1 CONSENT AND SCREENING

In order to participate in this Study, signed informed consent must be obtained from the Participant. The current IRB approved informed consent form must be signed and dated by each Participant prior to undergoing any Study procedures. The informed consent discussion must be documented, and a copy of their signed IRB approved informed consent form must be scanned in the Participant's medical record.

The Participant will be contacted with a targeted virtual communication message (i.e. MyChart message) that includes a brief purpose and summary of the Study with an included embedded link to self-screen through an nPhase REDCap Cloud survey for recruitment or by phone for patients who already have a scheduled visit with a dermatology Provider at the Study Site and meet Study inclusion criteria. Participants may also be recruited at health and/or wellness events in the community using a printed version of the approved virtual communication message with the included link to nPhase REDCap Cloud self-screening survey.

During this time, the Study Coordinators, under the supervision of the PI, will screen the Participants on nPhase REDCap Cloud to ensure they meet our eligibility criteria. Participants that complete the survey and meet the eligibility criteria will be contacted using the phone number provided in the screening survey and have their personal and contact information confirmed. Then a nPhase REDCap Cloud e-consent will be sent to the email given by the Participant. The Participants will be given ample time to review the consent form thoroughly and privately to avoid feeling pressured. If they indicate interest to participate in the Study and submit the nPhase REDCap Cloud screening and e-consent, they will be contacted by a Study Coordinator by phone to discuss in detail the consent form, what the Study entails, and answer any additional questions the Participant may have. If the Participant is unable to sign the e-consent form, they may be invited in-person to obtain written consent. If the subject does not respond after at least two call attempts made during the screening process over the span of a week, we will consider the subject as screen failed.

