## 5.5 PARTICIPANT DISCONTINUATION OR WITHDRAWAL

Participants are free to withdraw consent and discontinue participation in the Study at any time and without prejudice to further treatment. If a Participant withdraws consent, they should be asked to specify if they are withdrawing consent to all further participation in the Study or if they are choosing to withdraw only from further Study intervention, meaning that further follow-up and data collection about their disease and health status is allowable. The Participant should also be asked about their consent to the future use of their Study-generated data and any biological samples, as applicable.

No further Participant contact will be made if the Participant withdraws consent for participation in the Study. Information about the reason(s) for discontinuation will be collected at the time the Participant withdraws consent.

A Participant may also be withdrawn from the Study by the Investigator, local IRB, or regulatory authorities.

Reasons for a Participant to discontinue the Study may include the following:

- Participant dies or is lost to follow-up
- Participant withdraws consent for any further participation
- The end of Study is reached
- Significant Study intervention non-compliance
- If any clinical adverse event (AE), laboratory abnormality, or other medical condition or situation occurs such that continued participation in the Study would not be in the best interest of the Participant
- If the Participant meets an exclusion criterion (either newly developed or not previously recognized) that precludes further Study participation

In the event of a pregnancy, the Study intervention will be immediately reported to the appropriate committees and their participation in the Study will be discontinued. Refer to Section 10.6.6 regarding reporting of pregnancy

In the event a Participant withdraws early from the Study, Investigator(s) will attempt to find a replacement to enroll in the Study to meet target number of Participants.

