##### What should you do?

- a) **Self-monitor** the color, size or shape of this mole (skin lesion) after 1 month, then every 3 months. If you find that the mole changes at any time in the future you may re-scan the mole with Sklip Ai or consult with your local healthcare provider in person.
- b) **Submit** this mole today for a Sklip anonymous informational, non-diagnostic second opinion by a real dermatologist (additional fees may apply), or
- c) **Consult** this result in person with your established local healthcare provider if you do not understand this result or are still concerned about the mole. If you do not have an established provider click the **TAKE ACTION** button in this result to find a local dermatology office in the Sklip map.

*Costs associated with consulting your mole scan result with a healthcare provider are your financial responsibility and Sklip is not responsible for costs associated with medical care or verifying insurance coverage”*

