## 10. SAFETY

### 10.1 SPECIFICATION OF SAFETY PARAMETERS

The investigational device being assessed in this Study (Sklip System) is not of substantial importance in diagnosing, curing, mitigating, or treating disease. Instead, it provides a triage assessment according to a clinically accepted protocol, which is intended for confirmation by a healthcare professional. Therefore Participants enrolled in the Study are not exposed or introduced to any additional medical safety risks that would warrant scheduled screening assessments. The Participants have the option to be evaluated by a dermatology Provider via standard clinical care pathways, not part of the Study, and would be considered an unscheduled visit (Section 8.9 Unscheduled Visits).

There is minimal risk of psychological or behavioral effects that may be experienced by the Participant during the Study. At the start of enrollment for each Participant, he/she/they will have onboarding training by a Study Coordinator on how to contact a research team member to report any adverse psychological or behavioral effects throughout the duration of their enrollment.

If a Participant reports any adverse events, the investigator will immediately be informed of the event. The investigator will be responsible for assessing the reported adverse events and will be followed by a member of the Study team until resolution/stabilization. The Participant will be offered the voluntary option to withdraw from the Study and discontinue any intervention. The report will be documented in the Participant's record.

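### For participants without an existing appointment, the reference skin examination is booked after the SMSA result is seen, so verification can depend on the index test

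*Combined protocol and SAP*

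**What the plan says.** **Order of events.** In section 3.1 the participant obtains the SMSA output at step 9, records it at step 12, and at step 13 is told: "Contact the Study Site to schedule an in-person FBSE within 28 days, if the Participant does not already have a scheduled visit". Section 5.1 recruits partly "by phone for patients who already have a scheduled visit with a dermatology Provider at the Study Site", so some participants are booked before they scan; their share is not stated. Coordinators review charts every seven days to "track Participant requests to begin their In-person Phase" (section 3.1). No action is given for a participant who never makes the request.

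**What the participant has been told by then.** The UNREMARKABLE text in section 6.1.1 advises watching "the color, size or shape of this mole (skin lesion) after 1 month, then every 3 months", with an in-person consultation if the result is not understood or concern remains. The SUSPICIOUS text advises an in-person consultation, but allows an established local provider or any mapped dermatology office. Visit costs "will be billed by Study Sites directly to patient insurance, or required to be paid out pocket" (Synopsis).

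**Status of the visit.** The Synopsis says: "All Participants are required to come for an in-person FBSE, regardless of if they identify a PSLC during the At-home Phase". Sections 1.3.1, 3.2, 6.1.8 and 8.1.2 agree that the visit is mandatory. Section 8.9 only asks participants to attend. Section 10.1 says: "The Participants have the option to be evaluated by a dermatology Provider via standard clinical care pathways, not part of the Study". Section 8.7 states that there is no physical study visit.

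**Analysis.** Section 11.4.2 fills the true-positive and false-negative cells from biopsied lesions only (Dataset O). Section 3.1 has lesions without a biopsy read from the participant's dermoscopy image (Dataset E). Section 11.3 names an intent-to-treat set but gives no rule for a lesion without a reference result. Section 11.5 excludes imputation. No comparison of attendance by SMSA output is planned.

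**The concern.** In a diagnostic accuracy study, who receives the reference standard should not depend on the index-test result. Here the participant sees the result before arranging the reference visit, the app's advice differs by result, and the visit may cost the participant money. If attendance differs by output, the verified lesions are a selected sample and the 2x2 table is biased.

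The gap is most serious for a cancer called UNREMARKABLE in someone who does not attend. Without a biopsy it cannot enter the false-negative cell, and nothing in the analysis plan would show that it is missing. The same participant is the safety case: the Synopsis relies on the full body skin examination to catch malignancies that the At-home Phase misses.

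**Working it through.** **1. The plan's own figures.** Formula (1) in section 11.2 gives 1.96² × 0.974 × 0.026 / (0.10² × 0.023) = 422.98, i.e. 423 lesions. Then 423 / 1.5 × 1.10 = 310.2, i.e. 310 participants. Both reproduce. The 10% drop-out is a single figure, not split by SMSA output.

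**2. Inputs.** Table 6 expects 257 suspicious and 166 non-suspicious lesions of 423, so the UNREMARKABLE share is 166/423 = 39.2%. It expects 10 melanomas and 21 atypical nevi, together 31. The goals are 95% sensitivity for that group, 80% for squamous and for basal cell carcinoma, and 30% specificity. Attendance by output is not given; every split below is an assumption.

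**3. Formulas.** Let a+ be attendance after SUSPICIOUS and a− after UNREMARKABLE, with attendance unrelated to disease once the output is known.

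- Observed Se = Se·a+ / (Se·a+ + (1 − Se)·a−)
- Observed Sp = Sp·a− / (Sp·a− + (1 − Sp)·a+)

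Only the ratio a−/a+ matters. At 90%/90% both measures are unbiased.

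**4. All planned drop-out on UNREMARKABLE lesions.** This equates drop-out with non-attendance. Then a+ = 100% and a− = 1 − 0.10/0.392 = 74.5%. Solving back from the reported value:

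- Reported Se 95%: 0.95 × 0.745 / (0.95 × 0.745 + 0.05) = 93.4% true.
- Reported Se 80%: 0.80 × 0.745 / (0.80 × 0.745 + 0.20) = 74.9% true.
- Reported Sp 30%: 0.30 / (0.30 + 0.70 × 0.745) = 36.5% true.
- At the plan's 97.4%: 0.974 / (0.974 + 0.026 × 0.745) = 0.9805, a shift of about 0.65 points.

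**5. Range.**

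| Attendance SUSPICIOUS / UNREMARKABLE | True Se 95% reads as | True Sp 30% reads as |
|---|---|---|
| 90% / 90% | 95.0% | 30.0% |
| 95% / 80% | 95.8% | 26.5% |
| 100% / 74.5% | 96.2% | 24.2% |
| 95% / 60% | 96.8% | 21.3% |
| 80% / 95% | 94.1% | 33.7% |

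**6. In lesions.** With 31 target lesions and two false negatives, sensitivity is 29/31 = 93.5%. If one of the two is never verified it becomes 29/30 = 96.7%, across the 95% goal. This concerns the point estimate only. Even 31/31 gives a one-sided exact 95% lower bound of 0.05^(1/31) = 90.8%, so the bound cannot reach 95% at this size. Section 11.4.2 calculates both and does not say which is held against the goal.

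**The case against.** A reader might infer that this design does inflate sensitivity and lower specificity. The documents do not support that. They give no attendance by output, and the direction is open: SUSPICIOUS users may take the result to an outside provider and never reach the Study Site, which reverses the bias. UNREMARKABLE users chose these lesions because they were worried about them, and those still worried are told to consult in person. An examination within 28 days, set against the 3 to 6 month wait cited in section 1.3.2, is an incentive whatever the result.

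A reader might also infer that the visit is effectively optional. Five places say otherwise, and section 6.1.8 discloses both the requirement and the cost at onboarding. Under that text skipping is a deviation, and weekly chart review can show who has not booked. That lowers the likely rate of non-attendance. It does not remove the dependence on the result, and sections 8.7, 8.9 and 10.1 still contradict the requirement.

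Three further inferences go too far:

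- That a non-attender necessarily loses both image and histology. Section 3.1 allows images to be transferred by secure email, and a lesion without a biopsy needs only the participant's image. The specificity effect is therefore weaker. When UNREMARKABLE users attend less, it also errs against the device.
- That replacement refills the sample with attenders. Section 5.5 says only that "Investigator(s) will attempt to find a replacement to enroll in the Study to meet target number of Participants". Loss to follow-up is defined by the survey (section 5.6), so a non-attender who returns it need not be replaced. Replacements face the same booking order, so the attendance ratio does not change.
- That a false pass on the 95% goal is likely. In step 4, two expected false negatives lose 2 × 0.255, about half a lesion, and near the planned 97.4% the shift is small.

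Participants with a prior appointment are not exposed to the booking order, and mixed results within one participant (1.5 lesions expected) dilute the effect.

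**Conclusion.** The point holds as a conditional risk. For participants without an existing appointment, verification can depend on the SMSA output; a missed cancer in a non-attender cannot be counted; and no planned analysis would detect or correct this. The size rests on assumed attendance. With all planned drop-out on one side, sensitivity near the goals is overstated by about 1.6 points at a reported 95% (95 − 93.4) and 5.1 points at a reported 80% (80 − 74.9). With the opposite 80%/95% split, a true 95% is understated by 0.9 points. The sensitivity effect is firmer than the specificity effect, because the false-negative cell has no route other than the visit. The documents do not establish that the bias will occur or which way it will run. The case for acting is that the remedy is cheap before enrollment, while an unverified false negative cannot be recovered afterwards.

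**What to change.** 1. Set the examination date at onboarding, before SMSA access is issued and inside the existing visit window. Reword step 13 as attending the visit already booked.
2. Reconcile the passages on the status of the visit: the Synopsis and sections 1.3.1, 3.2, 6.1.8 and 8.1.2 against sections 8.7, 8.9 and 10.1.
3. Collect participant images remotely, together with the mole log that section 6.1.8 already has participants submit by upload or email.
4. Report attendance and availability of a reference result by SMSA output.
5. Prespecify a sensitivity analysis of the primary endpoints. Attendance belongs to the participant and the output to the lesion, so form two participant groups, any SUSPICIOUS and all UNREMARKABLE, and weight each attender's lesions by the inverse of the attendance rate in the group. Add a worst-case bound that counts every UNREMARKABLE lesion without a reference result as a false negative.

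Weighting cannot restore a false negative if none was observed in the group. The bound will be wide unless attendance is nearly complete: 310 × 1.5 = 465 enrolled lesions against 423 planned leaves 42 unverified, more than the 31 target lesions. Item 1 is therefore the main remedy, and items 4 and 5 show how well it worked.

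Cost: scheduling moves earlier with some rebooking, participants make one extra upload, and the report gains one table and one sensitivity analysis. No visits are added and the sample size does not change.

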**With dermatology Provider present:**

The dermatology Provider (DP) will be blinded to the skin lesions that were selected by the study Participant at home. The DP will perform a FBSE as part of the normal clinical care pathway. All PSLCs identified by the DP as SUSPICIOUS will be marked with a vertical line one (1) inch away from the target PSLC using a green surgical marker. After completing the FBSE and marking all DP-selected suspicious PSLCs, the DP will verbally inform the Study Coordinator the Participant's Fitzpatrick skin phototype (1,2,3,4,5 or 6) after leaving the patient room.

**Without dermatology Provider present,**

**with Study Coordinator present:**

The Participant will be asked to provide their Participant Mole Log Sheet (PMLS). Then, all PSLCs recorded in the PMLS will entered into REDCap Cloud by the Study Coordinator. Any Participant-selected PSLCs that match those identified earlier as SUSPICIOUS by the DP will be marked with a horizontal line one (1) inch away from the target PSLC using a green surgical marker. Therefore, PSLCs identified by both the DP and Participant will have a plus symbol. Next, the Study Coordinator will take and record (near-perfect) SCI and DDI for all PSLCs recorded in the PMLS and those PSLCs identified by the DP as SUSPICIOUS (not matching the Participant PSLCs). Then, the Study Coordinator will complete the following:

- 1) Take one (1) photo of the Participant identification sticker with a Study Site secure smartphone/tablet
- 2) Take one (1) smartphone clinical image (SCI) of each target PSLC recorded in the Participant Mole Log Sheet (PMLS)
- 3) Take one (1) digital dermoscopy image (DDI) of each target PSLC using the Sklip dermatoscope.
- 4) Save the DDI of the target PSLC in the Study Site smartphone/tablet native photo gallery
- 5) Upload the Study Coordinator-taken DDI to the SMSA ("Scan Moles with Ai") within the Sklip App
- 6) Take one (1) screenshot the SMSA output
- 7) Record each SMSA output (SUSPICIOUS, UNREMARKABLE, ERROR) in REDCap Cloud, per target PSLC
- 8) If the Participant has taken a set of SCI/DDI at home of a PSLC that is not intended (qualified because of anatomic body site) for the Sklip System, the Study Coordinator should still capture a set of control SCI/DDI and upload to REDCap Cloud. The Participant standard clinical care will not be changed.
- 9) If the Participant took a set of SCI/DDI of a PSLC at home but did not follow instructions – specifically uploading the DDI to the Sklip System - the Study Coordinator should remind the Participant to complete this task in the patient room (using the DDI from their mobile device gallery), upload to the Sklip System, and record the output on their Mole Log Sheet. If this situation occurs, the Study Coordinator should make a note in

REDCap Cloud; If the Participant is/was concerned about a PSLC but did not take a set of SCI/DDI at home, this PSLC will not be included in the study.

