**Schedule for data collection:**

In order to avoid Participant PSLC recollection-bias, Study Coordinators will use the Participant Mole Log Sheet (PMLS) and Participant taken SCI/DDI for guidance and **record** the following Datasets in REDCap Cloud:

- A) Total number of PSLCs identified by the Participant at-home
- B) Total number of PSLCs identified by the DP in-office
- C) One (1) individual SMSA output recorded in the PMLS, per target PSLC (SUSPICIOUS, UNREMARKABLE and ERROR)

Ensuring that no PHI is shared, Study Coordinators will **export** the following from the Participant smartphone/tablet gallery titled “Moles” to the Study Site smartphone/tablet gallery via Bluetooth or secure email:

- D) One (1) Participant-taken SCI, per target PSLC
- E) One (1) Participant-taken DDI, per target PSLC
- F) One (1) Participant-taken SMSA output screenshot, per target PSLC

Then, Study Coordinators will **acquire** and **export** the following from the Study Site smartphone/tablet gallery to an OHSU secure cloud storage service:

- G) One (1) Study Coordinator-taken DDI (near-perfect image technical quality) for each PSLC recorded in the PMLS and suspicious PSLCs identified by the DP in-office that were not recorded in the PMLS

Then, Study Coordinators will **upload** the DDI in Dataset (G) to the SMSA on a Study Site smartphone/tablet and **record** the following Datasets into REDCap Cloud:

- H) One (1) Study Coordinator-taken SMSA output for each PSLC, recorded in the PMLS, using Dataset (G) (SUSPICIOUS, UNREMARKABLE and ERROR), including one (1) screenshots

Then, the Study Coordinator will **record** the following Datasets into REDCap Cloud:

- I) All other SCI of suspicious PSLCs identified by the DP in-office that were not recorded in the PMLS
- J) All other DDI of suspicious PSLCs identified by the DP in-office that were not recorded in the PMLS
- K) Pathology reports for all PSLCs that were biopsied during the In-Person Phase
- L) Number of adverse events reported during the Study

-----End of In-person Phase-----

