#### 11.4.3 ANALYSIS OF THE EXPLORATORY ENDPOINTS

##### *Exploratory endpoint 1*

Similar to the Primary endpoint, the accuracy of SMSA output using Participant-taken DDI will be assessed using a 2x2 table, where the SMSA output of “SUSPICIOUS” or “UNREMARKABLE” will be compared to the SMSA output using Study Coordinator-taken DDI (near-perfect technical quality), simulating a laboratory-type environment where the SMSA is fed the near-perfect technical quality DDI.

The Sensitivity of the SMSA output from Participant-taken DDI will be compared to the Sensitivity of the SMSA output from Study Coordinator-taken DDI using McNemar’s Test, given the paired nature of the data, using 0.05 significance level.

The Specificity of the SMSA output from Participant-taken DDI will be compared to the Specificity of the SMSA output from Study Coordinator-taken DDI using McNemar’s Test, given the paired nature of the data, using 0.05 significance level.

This will be done for each disease entity:

- Melanoma and atypical melanocytic nevi with uncertain malignant potential,
- Squamous cell carcinoma,
- Basal cell carcinoma

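### The Study Coordinator sees the participant's SMSA result before capturing the comparison image for exploratory endpoint 1, and no retake or ERROR rule limits that capture

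*Combined protocol and SAP*

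**What the plan says.** At home, the participant is told to do the following (Section 3.1, step 12): "Record each SMSA output (SUSPICIOUS, UNREMARKABLE, ERROR) in the PMLS once per target PSLC". The log that comes to the visit therefore carries the first of the two SMSA results that exploratory endpoint 1 compares.

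The visit then runs in this order (Section 3.1, In-person Phase):

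- The dermatology provider examines the skin: "All PSLCs identified by the DP as SUSPICIOUS will be marked with a vertical line one (1) inch away from the target PSLC".
- The coordinator receives the log: "Then, all PSLCs recorded in the PMLS will entered into REDCap Cloud by the Study Coordinator".
- Lesions are matched to the provider's marks: "Any Participant-selected PSLCs that match those identified earlier as SUSPICIOUS by the DP will be marked with a horizontal line".
- Only then is the comparison image taken: "Next, the Study Coordinator will take and record (near-perfect) SCI and DDI for all PSLCs recorded in the PMLS".

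The schedule for data collection in Section 3.1 gives the same order by dataset. The coordinator records "C) One (1) individual SMSA output recorded in the PMLS, per target PSLC (SUSPICIOUS, UNREMARKABLE and ERROR" and exports "F) One (1) Participant-taken SMSA output screenshot, per target PSLC". After that come the coordinator's own dermoscopy image (Dataset G) and its SMSA output (Dataset H).

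The Synopsis and Section 5.3.1 blind the site PIs and dermatology providers to the at-home results. Neither names the coordinator, and Section 5.3.1 regards blinding as otherwise unnecessary because follow-up evaluation is standard care. In Section 11.4.3, the participant's output "will be compared to the SMSA output using Study Coordinator-taken DDI (near-perfect technical quality"), using McNemar's test for sensitivity and for specificity.

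**The concern.** Endpoint 1 is meant to isolate the user: the same lesion and the same algorithm, imaged by a layperson and by a trained operator. That contrast is cleanest if the second image is captured without knowledge of the first result. In the written order, the person producing the comparator already has the result it will be set against.

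The reason given for not blinding further, standard-care follow-up, does not reach this step, because coordinator imaging is a research procedure. Near-perfect has no stated acceptance criterion, so whether a capture is good enough is left to someone who knows the earlier answer. At stake is the interpretation of endpoint 1. The coordinator-output parts of endpoints 2 and 3 use the same Dataset H.

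**Working it through.** **1. Does the coordinator know the result before capture?** The sentence on log entry mentions lesions, not outputs, so it does not settle the question alone. Three other places do. Step 12 puts the output in the log. Datasets C and F are handled by the coordinator and listed before G and H. Section 6.1.8 asks participants to submit a copy of the log in advance by REDCap upload or email. No section withholds the output from the coordinator.

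**2. What discretion is left?**

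- Participants have a limit of three attempts (Section 3.1, step 9). The coordinator's steps give no attempt limit and do not say what to do after ERROR.
- Section 11.4.1 uses the first non-ERROR output, but that rule is worded for primary and secondary endpoints. The endpoints that follow it are primary and exploratory. The label may be a leftover, but as written the rule does not expressly cover endpoint 1.

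**3. Does it reach the primary endpoint?** No. That endpoint uses SMSA outputs from participant-taken images of lesions in the log. For unbiopsied lesions, the dermoscopic ground truth uses Datasets E and J: participant images, and coordinator images of provider-only lesions. For a lesion in the log, the coordinator's image enters neither side of the primary comparison.

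**4. How many pairs are there?** The plan's own figures reproduce first (Section 11.2):

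- n = 1.96² × 0.974 × 0.026 ÷ (0.10² × 0.023) = 422.98, i.e. 423 lesions.
- 423 ÷ 1.5 × 1.10 = 310.2, i.e. 310 participants.
- Table 6, melanoma: 423 × 0.023 = 9.7, i.e. 10.
- Table 6, atypical nevi: 413 × 0.05 = 20.7, i.e. 21.
- Positives in the combined entity: 10 + 21 = 31.

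**5. How sensitive is the test to one pair?** With b and c discordant pairs in the two directions, n = b + c and k = min(b, c), the exact two-sided p is 2 × Σ C(n, i) ÷ 2ⁿ for i = 0 to k. The plan does not say which version of McNemar's test will be used, so three are shown.

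| Discordant pairs | Exact | Uncorrected chi-square | Continuity-corrected |
|---|---|---|---|
| 5:0 | 2 ÷ 32 = 0.063 | 0.025 | 0.074 |
| 6:0 | 2 ÷ 64 = 0.031 | 0.014 | 0.041 |
| 6:1 | 2 × (1 + 7) ÷ 128 = 0.125 | 0.059 | 0.131 |

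One contrary pair added to 6:0 crosses 0.05 under all three versions. Losing one pair (6:0 to 5:0) crosses it under the exact and corrected versions only. Each pair is worth 1 ÷ 31 = 3.2 percentage points of sensitivity.

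This shows fragility and is not a forecast. The documents give no discordance rate, and 6:0 would itself be a difference of 6 ÷ 31 = 19.4 points. Table 6 expects more lesions elsewhere (52 and 121 in the two carcinoma columns, 220 negatives), so a single pair may matter less in those comparisons.

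**The case against.** The case against has force, and much of it stands.

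- **The reader is an algorithm.** The coordinator interprets nothing. Section 6.1.1 standardises capture (centring, zoom, oil, flat plate, gentle pressure), the SMSA checks image quality first, and one image and one output per lesion are specified. A reader might infer that the coordinator may choose among captures. The plan provides for no such choice, and repeating a capture because its result looked wrong would depart from the written steps. What remains is the execution of that one capture, plus the missing retake and ERROR rule.
- **McNemar's test does not need the two outputs to be independent.** It is built for correlated pairs, so the planned test is not invalidated. The issue is influence of one result on the other capture, not a failed assumption.
- **Direction is unproven.** A reader might infer that the coordinator's result is drawn toward the participant's and hides a user effect. It could equally be drawn toward the provider's mark, and where provider and participant output disagree, that would widen the difference. The documents settle neither.
- **Some knowledge cannot be removed.** Provider-only lesions must also be imaged, so the marks have to stay visible. The plan uses the log and the participant's images for guidance to avoid recollection bias; withholding those images would risk photographing the wrong mole and breaking the pairing.
- **The study is open-label and the endpoint exploratory.** That limits the weight of the point. It does not justify exposing the paired result when a change of order avoids it.

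**Conclusion.** The point holds in a limited form. The written order gives the coordinator the participant's SMSA output before the comparison image is captured, nothing blinds the coordinator to it, and no coordinator retake or ERROR rule closes the remaining discretion. The effect on the estimates cannot be sized from the documents, in magnitude or direction. The p-values above rest on Table 6's expected 31 lesions and on assumed discordant counts.

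A reader might go further and doubt the primary sensitivity and specificity results. The documents do not support that, because those results do not use coordinator captures of logged lesions. This is an inexpensive improvement to exploratory endpoint 1 and to the coordinator-output parts of endpoints 2 and 3. It does not affect the sample size or the primary analysis.

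**What to change.** Reorder the coordinator steps and the data-collection schedule in Section 3.1, and the matching Synopsis text:

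1. The coordinator works from lesion number, body site and the participant's clinical and dermoscopic images (Datasets D and E), kept for lesion matching. The SMSA output column and the result screenshots are withheld. The advance log copy in Section 6.1.8 is withheld from the imaging coordinator, or its output column is covered.
2. The coordinator captures and scans the comparison image and locks Dataset H in REDCap Cloud.
3. Only then are Datasets C and F opened and entered, and the step 9 check for missing participant scans done. That check uses an image already taken at home, so moving it does not affect the participant's capture.
4. Section 11.4.1 and the coordinator steps state that the three-attempt, first-non-ERROR rule also applies to coordinator scans.
5. The report states that coordinator capture was not blind to the provider's marks.

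The cost is a slightly split data-entry step and a log sheet with a detachable or covered output column. Screenshots now go into the same phone album as the lesion images, so they would need a separate album or a second export. Sample size, tests and clinical care do not change. If the reorder is not adopted, the interpretation of endpoint 1 should say that capture was made with the participant's result known.
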